9.4 Subsequent visits

**University of
Nottingham**
Health Service

At day 28 and 168 after visit 1, participants will be asked to provide a further 15ml blood sample to measure immunological and biochemical responses.

Participants in the optional immunology subgroup cohort may be invited to have a larger blood sample (up to 60ml) collected at day 28.

A qualitative nested interview study will be used to assess participants', clinicians' and other stakeholders' views on intervention and trial acceptability and determine the barriers and facilitators to implementing the intervention in routine care. The process for obtaining participant informed consent for the study will include consent for potential inclusion in the qualitative interview nested study. The qualitative study will be reported in line with the Consolidated Criteria for Reporting Qualitative Research (COREQ: Tong et al, 2007).

We will conduct semi-structured interviews with a sample of patient participants and stakeholders (healthcare professionals, or other practice staff involved in explaining the trial to patients, conducting the screening and consent processes, or delivering the intervention). We aim to complete these within 4 weeks of the end of the intervention period. Interviews will be conducted by telephone, video call or face-to-face at participant preference, audio-recorded (with permission) and transcribed verbatim. Topic guides will be developed based on study aims and input from the Trial Management Group (TMG). Interview participants will be selected purposively to ensure diversity in relevant characteristics (e.g., trial group allocation, age, gender, ethnicity, deprivation index, region). Sampling will cease when we have sufficient information power relevant to the study aims (Malterud et al, 2016) although we anticipate up to 20 participants, and 10 stakeholders. Analysis of qualitative data will use appropriate methods such as inductive thematic analysis.

9.5 Sample collection and storage

Sample collection, handling and storage will be described in the laboratory analysis plan and the relevant site-specific SOPs.

9.6 Laboratory analysis

Blood Samples will be assessed for a variety of immunological parameters relevant to vaccine responses (e.g., IgG antibody levels). They may also be analysed for other immunological parameters relevant to the immune and endocrine response to vaccination (e.g., cytokines). The analyses will be conducted by the study team, overseen by [name]. These analyses will be completed at the University of Nottingham using equipment and laboratories serviced and managed at the University of Nottingham.

**University of
Nottingham**
Health Service

Serum vitamin D levels will be measured at each time point. This analysis will be undertaken at Nottingham University Hospital Biochemistry laboratories which is a fully accredited NHS facility.

9.7 Compliance

Compliance is defined as the proportion of participants that complete diary, receive at least one dose of the SARS-CoV-2 vaccine and provide a pre-vaccination and at least one post-vaccination blood sample.

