Finally, we will also interview a small number of participants as well as people working in vaccine clinics to gain their views on our approach to improving vaccine effectiveness. This work will help to identify if there is an easy and effective way to make vaccines work better that is acceptable to doctors and patients, doesn't have any side effects and which anyone, anywhere can try.

4. Synopsis

Study title	A feasibility randomised controlled trial examining the effect of a positive mood intervention and vitamin D supplementation on the immunological responses to a boosting COVID-19 and/or influenza vaccination in healthy adults		
IRAS reference	316876		
Short title	PROTECTIVE-D: imPROving the effecTivenEss of vaccinaTion wltH positive mood and Vitamin D		
Participants	Adults aged 65 years and over eligible for COVID-19 booster vaccination in Autumn 2022		
Sample size	~40		
Treatment	Positive mood intervention +/- vitamin D supplementation		
Treatment duration	7-28 days		
Study duration	12 months		
Planned study period	November 2022 to November 2023		
Objectives	Outcome measures	Evaluation time points	
Primary	Feasibility and acceptability of study interventions for testing in future studies	Qualitative assessment of acceptability of interventions. Intervention adherence measures.	4 weeks

**University of
Nottingham**
Health Service

Exploratory	Assessment of effectiveness of study intervention in improving immune response to COVID-19 boosting and/or influenza vaccination.	Anti-SARS-CoV-2 immunoglobulin levels +/- vaccine induced influenza immunoglobulin levels	4 weeks 24 weeks
	Further investigate immunological response to intervention.	SARS-CoV-2/influenza neutralising antibodies and T-cell responses.	4 weeks

**University of
Nottingham**
Health Service

5. Abbreviations

AE:	Adverse Event
AR:	Adverse Reaction
CI:	Chief Investigator
CRF:	Case Report Form
CTIMP:	Clinical Trial of Investigational Medicinal Product
DSUR:	Development Safety Update Report
EudraCT:	European Clinical Trial Database
FDA:	Food and Drug Administration
GCP:	Good Clinical Practice
GDPR:	General Data Protection Regulation
HRA:	Health Research Authority
ICF:	Informed Consent Form
ISF:	Investigator Site File
PI:	Principal Investigator
PIS:	Participant Information Sheet
PPI:	Patient and Public Involvement
REC:	Research Ethics Committee
SAE:	Serious Adverse Reaction
SAE:	Serious Adverse Event
SOP:	Standard Operating Procedure
SUSAR:	Suspected Unexpected Serious Adverse Reaction

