8.1 Study participants

Adults aged 65 and over who will be receiving an invitation to a COVID-19 or COVID-19 and influenza vaccination appointment at their GP Practice and/or mass vaccination clinic as per UK government guidance in autumn **2022 or 2023** will be eligible to participate in this study.

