8.2 Inclusion criteria

- Participants must be able and willing to provide written informed consent to participate in the study.
- Participants must be able and willing (in the investigator's opinion) to comply with all the study requirements.
- Participants must consent to allow investigators to discuss their medical information with their general practitioner and access medical records where relevant to the study.
- Eligible to receive a COVID-19 vaccination and/or influenza vaccination as part of usual care.

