9.3 Enrolment visit

- Informed consent and eligibility will be checked by the research team (PIs, research nurse or practitioner).
- Demographics and medical history will be collected.
- Participants will be randomly allocated to one of the 4 study groups in a 1:1:1:1 ratio.
- Randomisation will be performed by an electronic randomisation system.
- Participants will provide a 15ml venous blood sample for biochemical and immunological analysis. A subgroup of participants will be invited to have a maximum 60ml blood sample taken for further immunological analysis. Venous blood samples will be collected by a phlebotomy trained Research Nurse/Practitioner using a vacutainer system or syringe and butterfly.
- Participants randomised to the positive mood intervention will receive a 15 minute positive mood intervention consisting of a combination of positive mood stimuli previously shown to enhance mood in older adults. Participants will also receive information on how to access their positive mood intervention over the next 6 days. Daily reminders to complete the intervention and e-diary will be sent via secure SMS messaging and checked by the PI and/or Research Nurse. In the event a participant is unable to work the e-diary, alternatives can be provided, such as paper copies or phone calls.
- Participants randomised to standard over the counter vitamin D supplement, will be advised to buy and take this immediately prior to vaccination and once daily for the following 27 days. Reminders will be sent to complete the intervention and e-diary as for the positive mood intervention group.
- Participants will then receive their COVID-19 booster and influenza vaccination in the standard NHS clinic which will be running at the site on that day. The vaccine will not be given as part of the study and the type of vaccine, timing or method will not be impacted by their participation in the study.

Some participants, clinicians' and other stakeholders' will then be interviewed about the intervention and trial acceptability and determine the barriers and facilitators to implementing the intervention in routine care. Interviews will be conducted by telephone, video call or face-to-face at participant preference, audio-recorded (with permission) and transcribed verbatim.

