11.1 Sample Size Determination

We do not specify *a priori* sample size since we will be assessing recruitment, study procedures and retention in order to inform the planning of a larger trial at a future date. We will pause recruitment when we have a minimum of 10 participants in each arm (about 40 participants in total).

At that point we will perform an interim analysis of both the quantitative and qualitative data obtained and determine whether we have enough outcome measures to meet the primary objective. This decision will be taken by the study steering group which will comprise all of the investigators and the study co-ordinator. The decision will be based on whether the data obtained is sufficient to fully inform the design of the larger trial to follow, specifically whether the methodology is acceptable to participants and study staff and whether the intervention adherence measures are capturing data as intended. We have expertise in qualitative methodology in the study steering group.

If the group feel that we have sufficient data to achieve the primary objective, the study will be stopped and the exploratory outcome data will be analysed. If the group feel further data is needed, we will not analyse exploratory outcome data at this point and recruitment will resume until a minimum of 20 patients per arm have been recruited (about 80 participants in total). When data collection is complete, we will perform a final analysis of all primary and exploratory outcome data.

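### The compliance rule in section 9.7 contains no measure of intervention use and fails any participant vaccinated against influenza only

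*Protocol*

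**What the plan says.** Section 9.7 of the protocol gives the definition: "Compliance is defined as the proportion of participants that complete diary, receive at least one dose of the SARS-CoV-2 vaccine", and, as a further condition, that they "provide a pre-vaccination and at least one post-vaccination blood sample". All parts must be met. No other section defines compliance or adherence.

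The Synopsis (section 4) lists the primary outcome measures, assessed at 4 weeks, as "Qualitative assessment of acceptability of interventions. Intervention adherence measures". Section 11.1 makes the decision at about 40 participants depend partly on "whether the intervention adherence measures are capturing data as intended". It also says that "we will be assessing recruitment, study procedures and retention in order to inform the planning of a larger trial".

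On which vaccine qualifies, the sections differ:

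- Section 8.2 admits those "Eligible to receive a COVID-19 vaccination and/or influenza vaccination as part of usual care". The Plain English Summary (section 3), Methods (section 7) and section 9.2 also allow influenza vaccination alone.
- Section 8.1 describes "Adults aged 65 and over who will be receiving an invitation to a COVID-19 or COVID-19 and influenza vaccination appointment". The participants line of the Synopsis names only the COVID-19 booster.
- Section 9.3 says "Participants will then receive their COVID-19 booster and influenza vaccination in the standard NHS clinic", as if everyone receives both.

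**The concern.** A feasibility trial with adherence as a primary outcome needs to know how much of each intervention was used. The one rule that the protocol fixes counts diary completion, vaccination and blood sampling. On its wording, a participant who completes the diary but takes no vitamin D is compliant, and one who takes every dose but leaves the diary incomplete is not. Non-use is a practical possibility, because section 9.3 asks participants to buy the supplement themselves.

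The vaccine term is a second problem. A person who enters under the wording of 8.2 for influenza vaccination alone is non-compliant by construction, however well they follow the study. If the 9.7 proportion is reported as it stands, it can be too high as a reading of adherence and too low as a reading of procedural compliance, and the reader cannot tell which.

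**Working it through.** **Inputs.** Allocation 1:1:1:1 (section 7). Planned size: at least 10 per arm, 4 × 10 = 40; if extended, at least 20 per arm, 4 × 20 = 80 (section 11.1). Exposure: 7 days of mood intervention and 28 days of vitamin D, each counting the day of vaccination (section 7). The protocol states no compliance or adherence figure, so there is none to reproduce.

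**Step 1: does intervention use enter the rule?** Read as written, compliance C requires a completed diary (share d), a SARS-CoV-2 dose (v) and the blood samples (b). If these are independent, C = d × v × b. Intervention use u does not appear. With assumed d = 0.90, v = 1 and b = 0.90, C = 0.90 × 1 × 0.90 = 0.81 at u = 0%, 50%, 80% or 100%. In practice non-users may also skip the diary, so C could move with u indirectly. That would reflect behaviour and is not something the rule measures.

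**Step 2: the vaccine term.** Let f be the share vaccinated against influenza only. The documents do not give f. With perfect conduct otherwise, the maximum is C = 1 − f.

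| Assumed f | Maximum C | Of 40 | Of 80 |
|---|---|---|---|
| 0% | 100% | 40 | 80 |
| 10% | 90% | 36 | 72 |
| 25% | 75% | 30 | 60 |
| 50% | 50% | 20 | 40 |

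The first row applies if 8.1, 9.3 and the Synopsis participants line govern entry. The others are possible only if sections 3, 7, 8.2 and 9.2 govern.

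**Step 3: the diary term in usual care.** Sections 7 and 9.3 describe the e-diary alongside reminders for the interventions. Section 11.3 builds its full data set from those who complete the e-diary and sets no limit by arm. Whether usual care has a diary is therefore unclear. If it has none, one of four equal arms cannot meet 9.7, and the overall maximum is 3/4 = 75% (30 of 40, or 60 of 80). The same reading would leave usual care out of the 11.3 data set.

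**Step 4: the sample term.** Section 9.4 takes follow-up blood at day 28 and day 168. One sample after vaccination is enough for 9.7, so day 168 alone satisfies it, although the primary evaluation is at 4 weeks. The composite does not show retention at either visit.

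**Step 5: what separate reporting would give.** Each intervention is allocated to two arms, so its denominator is 20 at N = 40 and 40 at N = 80. For illustration, if 80% were classed as adherent, the exact (Clopper-Pearson) 95% interval is 56.3% to 94.3% for 16 of 20, and 64.4% to 90.9% for 32 of 40.

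**The case against.** The strongest reply is that 9.7 is not meant to measure adherence. The Synopsis and 11.1 speak of intervention adherence, while 9.7 speaks of compliance and lists study procedures. Section 9.8 uses the word in the same procedural sense. The scoring of adherence may sit in a statistical analysis plan or diary specification that is not shown, and serum vitamin D, measured at each time point under 9.6, is a further source. This stands in part. A reader might infer that 9.7 is the primary adherence measure, so that the primary question cannot be answered. The documents do not say so, and adherence data may well be collected.

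Other stronger readings also go beyond the text:

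- **That the go/no-go for the larger trial rests on an adherence level.** Section 11.1 decides whether to stop at about 40 or continue to about 80. It looks at whether the data are sufficient, whether the methods are acceptable and whether the adherence measures work. It sets no threshold and does not cite 9.7.
- **That usual care cannot comply.** This holds only if that arm has no diary, which is not established.
- **That the composite hides recruitment.** Recruitment is not one of its components, and 11.1 says that it will be assessed.
- **That a mood-arm participant could comply with no sessions at all.** The first session is delivered at the enrolment visit (9.3), so this is not a realistic case.
- **That influenza-only participants would have no antibody outcome.** All participants are asked for blood, the Synopsis provides for influenza antibodies, and 11.3 includes laboratory data from everyone enrolled.

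The reply does not remove two facts: the only fixed rule has no intervention-use term, and its vaccine term conflicts with the inclusion criterion.

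**Conclusion.** The point holds in a limited form. The absence of an intervention-use term follows from the text and needs no assumption: the 9.7 proportion says nothing about use of either intervention and should not be presented as adherence. The conflict between the vaccine term and the inclusion criterion is also textual. Its size depends on f, which is not given: no effect at f = 0, and a ceiling of 1 − f otherwise. The 75% ceiling for the diary term depends on usual care having no diary. All percentages here are illustrations under stated assumptions and do not predict the trial's result. The protocol itself has to settle the vaccine wording, because it sets eligibility.

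**What to change.** 1. In 9.7, replace the SARS-CoV-2 dose requirement with receipt of the study-qualifying vaccine(s) that the participant was due. Reconcile the vaccine-eligibility wording across the Synopsis, 8.1, 8.2, 9.3 and 9.7. The investigators must decide whether influenza-only participants may enter; this review takes no side.
2. Report intervention adherence separately from procedural compliance: days of use recorded out of 7 for the mood intervention and out of 28 for vitamin D, each among all participants allocated to that component. Use the serum vitamin D already measured under 9.6 as supporting evidence. Report sample retention at day 28 and at day 168 among all randomised.
3. State whether usual care completes the diary. If it does not, do not require it of that arm in 9.7, and check 11.3 for the same requirement.

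The cost is protocol wording and slightly more tabulation. The adherence measure assumes that the e-diary records daily use, which the protocol does not state, so the diary content needs confirming. Use that is not recorded would still be missed by the diary measure; serum vitamin D offers a partial check for that component only.

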9.8 Discontinuation/withdrawal of participants

Each participant may exercise their right to withdraw from the study at any time. In addition, the investigator may terminate the participant's involvement in the study at any time if the investigator considers it necessary for any reason including, though not exclusive to, the following:

- Ineligibility (either arising during the study or in the form of new information not declared or detected during the eligibility assessment)
- Significant protocol deviation
- Significant non-compliance with study requirements
- Any adverse event which requires discontinuation of the study procedures or results in an inability to continue to comply with study procedures
- Consent withdrawn
- Lost to follow up

The reason for withdrawal will be recorded in the study records, the withdrawn participants will not be replaced. Withdrawal from the study will not result in exclusion of the data generated by that participant from analysis unless requested by the participant.

9.9 Definition of end of study

The end of the study will be defined as the time the last blood sample is analysed.

10. Safety reporting

Safety reporting for participants in this study begins at the point of consent and ends at 168 days post-enrolment. Safety data will be collected via:

- Direct notification by the participant to the investigator via email or telephone according to the information on the study contact card given to each participant at enrolment.
- Investigator review of primary care medical records at 28 days and 168 days.

All serious adverse events that have not resolved by the end of the study, or that have not resolved upon discontinuation of a subject's participation in the study, must be followed until any of the following occurs:

- The event resolves
- The event stabilises
- The event returns to a baseline if a baseline value is available
- The event can be attributed to agents other than to study interventions or to factors unrelated to study conduct
- It becomes unlikely that any additional information can be obtained (participant or health care practitioner refusal to provide additional information, lost to follow-up after demonstration of due diligence with follow-up efforts)

10.1 Adverse event definitions

Adverse Event (AE)	Any untoward medical occurrence in a participant to whom a medicinal product has been administered, including occurrences which are not necessarily caused by or related to that product.
Adverse Reaction (AR)	An untoward and unintended response in a participant to an investigational medicinal product which is related to any dose administered to that participant. The phrase "response to an investigational medicinal product" means that a causal relationship between a trial medication and an AE is at least a reasonable possibility, i.e., the relationship cannot be ruled out. All cases judged by either the reporting medically qualified professional or the Sponsor as having a reasonable suspected causal relationship to the trial medication qualify as adverse reactions.

**University of
Nottingham**
Health Service

Serious Adverse Event (SAE)
	
A serious adverse event is any untoward medical occurrence that:
 
 • results in death • is life-threatening • requires inpatient hospitalisation or prolongation of existing hospitalisation • results in persistent or significant disability/incapacity • consists of a congenital anomaly or birth defect*. 
Other 'important medical events' may also be considered a serious adverse event when, based upon appropriate medical judgement, the event may jeopardise the participant and may require medical or surgical intervention to prevent one of the outcomes listed above.
 
NOTE: The term "life-threatening" in the definition of "serious" refers to an event in which the participant was at risk of death at the time of the event; it does not refer to an event which hypothetically might have caused death if it were more severe.
 
NOTE: Pregnancy is not, in itself an SAE, but an adverse outcome of pregnancy, for example spontaneous miscarriage, may be judged to be an SAE if clinically appropriate.

Serious Adverse Reaction (SAR)
	
An adverse event that is both serious and, in the opinion of the reporting Investigator, believed with reasonable probability to be due to one of the trial treatments, based on the information provided.


Suspected Unexpected Serious Adverse Reaction (SUSAR)
	
A serious adverse reaction, the nature and severity of which is not consistent with the Reference Safety Information for the medicinal product in question set out:
 
 • in the case of a product with a marketing authorisation, in the approved summary of product characteristics (SmPC) for that product • in the case of any other investigational medicinal product, in the approved investigator's brochure (IB) relating to the trial in question.

10.2 Assessment of causality

**University of
Nottingham**
Health Service

Causality will be clinically assessed relative to the interventions administered during the trial by the Chief Investigator. An adverse event is considered to have a causal relationship to an intervention if the attribution is possible, probable, or very likely by the definitions listed below. An adverse event is considered to have no causal relationship to an intervention if the attribution is not related or unlikely by the definitions listed below. In the group receiving two interventions, the attribution of any adverse event to either of the individual interventions will be at the Chief Investigator’s discretion.

Causality term	Assessment criteria
0 No relationship	No temporal relationship to study product and Alternate aetiology (clinical state, environmental or other interventions); and Does not follow known pattern of response to study product
1 Unlikely	Unlikely temporal relationship to study product and Alternate aetiology likely (clinical state, environmental or other interventions) and Does not follow known typical or plausible pattern of response to study product.
2 Possible	Reasonable temporal relationship to study product; or Event not readily produced by clinical state, environmental or other interventions; or Similar pattern of response to that seen with other vaccines
3 Probable	Reasonable temporal relationship to study product; and Event not readily produced by clinical state, environment, or other interventions or Known pattern of response seen with other vaccines
4 Definite	Reasonable temporal relationship to study product; and Event not readily produced by clinical state, environment, or other interventions; and Known pattern of response seen with other vaccines

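### Sections 10.1 and 10.2 use different causality thresholds and assessors, so a serious event graded Possible is causal under 10.2 yet need not be classed as a SAR or SUSAR under 10.1

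*Protocol*

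**What the plan says.** Section 10.1 defines the reaction classes. An AR exists when "a causal relationship between a trial medication and an AE is at least a reasonable possibility", which the section explains as a relationship that cannot be excluded. The suspicion of either the reporting medically qualified professional or the Sponsor is enough. A SAR is a serious event "believed with reasonable probability to be due to one of the trial treatments", and here the opinion that counts is the reporting Investigator's. A SUSAR is a SAR that does not fit the reference safety information.

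Section 10.2 gives the causality assessment to the Chief Investigator and sets the cut-off: "An adverse event is considered to have a causal relationship to an intervention if the attribution is possible, probable, or very likely". The other side is "An adverse event is considered to have no causal relationship to an intervention if the attribution is not related or unlikely". In the table below that text, *Possible* lists its criteria as alternatives: "Reasonable temporal relationship to study product; or Event not readily produced by clinical state, environmental or other interventions; or Similar pattern of response". *Unlikely* lists its criteria as joint conditions, beginning "Unlikely temporal relationship to study product and Alternate aetiology likely". *No relationship* is also a joint list and begins with the absence of a temporal relationship.

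Section 10.4 sends SAEs to the Chief Investigator with no causality condition, requires a form for every reportable SAE, and limits causality assignments to vitamin D and the positive mood intervention.

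**The concern.** The three definitions form a chain: a SUSAR must be a SAR, and a SAR is a serious event with a causal link. The link is worded more strictly for the SAR than for the AR, and more strictly than the 10.2 cut-off. On the plain wording, the more serious class therefore has the harder test. The person whose opinion decides also changes from row to row, and no passage says which opinion prevails when they differ.

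What is at stake is classification. Expectedness is considered only for a SAR. If an event is causal under one section but not a SAR under the other, two careful readers can file it differently, and one of them will not test it for expectedness.

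A second, smaller matter lies in the table. All participants have their usual-care vaccine at the enrolment visit, and vitamin D is to be taken just before it. An ordinary vaccine reaction will therefore have reasonable timing relative to vitamin D, and the table appears to leave no grade below *Possible* for it.

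**Working it through.** No figure in the protocol bears on this point, so there is none to reproduce. The check sets the passages side by side and then enumerates the table.

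**1. Threshold and assessor**

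| Place | Applies to | Causal threshold | Whose judgement |
|---|---|---|---|
| 10.1, AR | any event | reasonable possibility, not excluded | reporting professional or Sponsor, either one |
| 10.1, SAR | serious events | reasonable probability, not defined further | reporting Investigator |
| 10.1, SUSAR | a SAR that is unexpected | inherited from SAR | inherited from SAR |
| 10.2 | any event | *Possible* or higher | Chief Investigator |
| 10.4 | SAEs | none needed to reach the Chief Investigator | not applicable |

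**2. One event followed through.** Take a serious event that the Chief Investigator grades *Possible*.

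- Under 10.2 it is causal, because *Possible* is above the cut-off.
- Under the AR row it can be an AR, because a relationship "is at least a reasonable possibility, i.e., the relationship cannot be ruled out" is the whole test.
- Under the SAR row the reporting Investigator must hold that it is reasonably probable. An event that is only possible need not meet that.
- If it is not a SAR, it cannot be a SUSAR, so the question of expectedness does not arise.
- Under 10.4 it is still an SAE and still goes to the Chief Investigator.

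**3. The grading table.** Let T = reasonable timing, N = not readily produced by other causes, P = similar or known pattern. There are 2 × 2 × 2 = 8 combinations.

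- *Possible* = T or N or P. This holds in 7 of 8, that is, in all except T = N = P = 0.
- *Unlikely* and *No relationship* need every element to point away from the product. Only T = N = P = 0 qualifies, 1 of 8.
- *Probable* joins its criteria with an and followed by an or, so it can be read as (T and N) or P, or as T and (N or P). Timing alone (T = 1, N = 0, P = 0) meets neither reading.
- *Definite* = T and N and P, 1 of 8.

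Timing alone is thus exactly *Possible*, and 10.2 counts it as causal. The enumeration simplifies in treating the lower grades' aetiology and pattern conditions as the opposites of N and P. The result on timing does not depend on this: both lower grades require absent or unlikely timing, so T = 1 rules them out whatever N and P are. Nothing in the table separates serious from non-serious events.

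**The case against.** **The phrase is undefined.** The protocol does not say what reasonable probability means. An investigator may take it as equivalent to reasonable possibility, and then no event is classified differently. This stands: the loss of SAR status is a risk under the natural reading, not a certain result.

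**A broad *Possible* is consistent with the AR definition.** Section 10.1 counts a relationship that cannot be excluded, and an inclusive *Possible* carries that out. This also stands. Requiring that no other cause be more likely would make some events ARs under 10.1 and non-causal under 10.2, so that change is not proposed. What remains is that the literal table offers no lower grade even when another cause is evident. Section 10.2 does call the assessment clinical, so an assessor may not apply the table mechanically.

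**Section 10.4 may seem to settle vaccine reactions.** It covers only SAEs after externally given vaccines or medicines, and calls them unrelated to a study vaccine. It does not say they are unrelated to vitamin D or to the mood intervention.

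A reader might infer three stronger things that the protocol does not support:

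- *That serious events graded Possible are lost from safety reporting.* They remain SAEs, reach the Chief Investigator and are recorded on the SAE form if reportable. Only the SAR or SUSAR label is exposed.
- *That over-attribution affects only non-serious events.* The 10.2 rule covers any adverse event.
- *That related-event counts will show a false excess with vitamin D.* The protocol plans no comparison of related events between arms. Attribution also applies to the mood intervention, so only usual care has nothing to relate an event to. No event rates are given from which to size an excess.

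**Conclusion.** The inconsistency is real and lies in definitions that the protocol itself fixes, so it is not a matter left to an analysis plan. Sections 10.1 and 10.2 use two thresholds (possibility and probability) and name three sources of judgement (Chief Investigator; reporting Investigator; reporting professional or Sponsor) without a rule to choose among them. The consequence is limited to whether a serious event graded *Possible* is classed as a SAR and then assessed for expectedness. It rests on reading reasonable probability as stricter than reasonable possibility, which is the ordinary sense of the words.

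No count of affected events can be given. The study is a feasibility trial of about 40 participants, or about 80 if recruitment resumes, and the point does not touch its primary objective. It is worth correcting because it concerns safety classification and the correction is short.

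The table's treatment of well-timed events is secondary: 7 of 8 combinations count as causal, and a well-timed event of any seriousness cannot be graded lower. This calls for the table to be reconciled with the AR definition, not for a stricter *Possible*.

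**What to change.** - In 10.1, use one causal threshold for AR and SAR, namely at least a reasonable possibility, and state that it corresponds to *Possible* or higher in 10.2. The SUSAR definition then follows without change.
- State one rule for whose judgement counts. For example, an event is related if either the reporting investigator or the Chief Investigator/Sponsor judges it so. Check 10.4 against this rule: it lets the Chief Investigator decide whether the Sponsor is told, and a Sponsor judgement can count only for events the Sponsor sees.
- Reconcile the 10.2 table with the AR definition, so that it is clear how to grade a well-timed event whose relationship to the intervention can be excluded because another cause, such as the vaccine given at the same visit, is evident.
- While editing, make the grade names agree (the text has a *very likely* grade and a *not related* grade; the table has *Definite* and *No relationship*) and resolve the ambiguous and/or in *Probable*.

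The cost is a few lines in 10.1 and 10.2, with a matching check of 10.4. The small downside is that a few more serious events will be assessed for expectedness.
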